4.0 TREATMENT PLAN

4.1 Treatment Dosage and Administration

The investigational treatment is Everolimus; it will be administered in conjunction with best supportive care. Best supportive care includes all care provided to patients deemed necessary by the treating physician, such as analgesics and anti-diarrheal therapies.

- Everolimus will be administered by mouth at a starting dose of 4.5 mg/m²/day. Each course of therapy will last for 28 days for up to 24 courses.
- The starting dose 4.5 mg/m² of Everolimus will be titrated upward (or downward), subject to tolerability, with the objective of achieving trough Everolimus levels in the range of 5-15 ng/mL.
- All dosages prescribed and dispensed to the patient and all dose changes during the study must be recorded.
- Medication labels will comply with US legal requirements and be printed in English. Additional labels may be used in the primary language of the study participant. They will supply no information about the patient. The storage conditions for Everolimus will be described on the medication label.

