4.3 Medication Formulations, Dosage and Administration

- 4.3.1 Everolimus is supplied by Novartis. Everolimus should be administered orally, once daily at the same time every day either consistently with food or consistently without food. Everolimus is available as dispersible tablets.
- 4.3.2 The dose of Everolimus is 4.5 mg/m²/day administered once a day. The initial calculated dose of Everolimus will be rounded either up or down to the nearest possible dose based upon available Dispersible Tablets (see section 4.4.3 below).
- 4.3.3 Everolimus will be supplied in the form of Dispersible Tablets (also referred to as 'tablets for oral suspension'): 2 mg, 3 mg and 5 mg.
- 4.3.4 Everolimus may be administered by either of the following two methods:
- 4.3.5 **Method 1, Using an oral syringe:** The required number of dispersible tablets (maximum of five 2 mg tablets, three 3 mg tablets, or two 5 mg tablets) should be placed into a 10 mL oral syringe. The plunger should be inserted and pushed inward to make contact with the dispersible tablet(s). A sufficient volume of water (approximately 5 mL) should be drawn up from a glass to cover the dispersible tablet(s). In addition, approximately 4 mL of air should be drawn up into the oral syringe. The filled oral syringe should be placed in a glass (tip up) and the contents left to disintegrate for 3 minutes. Prior to administration, the oral syringe should be inverted gently five times. While holding the oral syringe in an upright (tip up) position, excess air should be removed carefully. The full contents of the oral syringe should be immediately dispensed into the mouth of the patient, slowly and gently. The same volume of water and air should then be drawn up into the oral syringe, and the contents should be swirled to suspend any remaining particles. The contents should be administered as previously described to ensure the entire dose is administered.

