4.5 Recommended Dose of Everolimus

The recommended starting dose is 4.5 mg/m²/dose, once daily. Continue treatment for up to 2 years, until disease progression or unacceptable toxicity occurs. After 2 years of therapy, patients will complete the study protocol, but may continue therapy using commercially available drug based upon the clinical judgment of their treating physician and the child's parents or guardians.

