AST or ALT elevation Grade 4 (> 20 x ULN)*	Interrupt Everolimus administration until resolution to ≤ grade 1 (or ≤ grade 2 if baseline values were within the range of grade 2). If resolution occurs ≤ 7 days, Everolimus should be re-started at one dose level lower. If resolution takes > 7 days, discontinue Everolimus.
Recurrence of Grade 4 AST or ALT elevation after dose reduction or toxicity requiring Everolimus interruption for > 28 days	Discontinue Everolimus.
Intolerable grade 2 mucositis, or grade 3 AE, except hyperglycemia or hypertriglyceridemia or hypercholesterolemia	Interrupt Everolimus administration until resolution to ≤ grade 1 or baseline grade / value. If resolution occurs within ≤ 7 days, Everolimus should be re-started at the dose level prior to interruption. If resolution takes > 7 days, or if event recurs within 28 days, hold Everolimus until recovery to ≤ grade 1 or baseline grade / value and reintroduce Everolimus at one dose level lower, if available. Patients will be withdrawn from the study if they fail to recover to ≤ grade 1 or baseline grade / value within 28 days.
Any other grade 4	Hold Everolimus until recovery to grade ≤ 1 or baseline value Reintroduce Everolimus at one dose level lower, if available.
Grade 3 or 4 clinical liver failure (asterixis or encephalopathy/coma)	Discontinue Everolimus
Recurrence of intolerable grade 2 mucositis or grade 3 event after dose reduction	Reduce dose to the next lower dose level, if available. The lowest possible dose level of Everolimus is 2 mg daily. Below this level, Everolimus must be discontinued.
Recurrence of grade 4 after dose reduction	Discontinue Everolimus
Any non-hematologic toxicity requiring Everolimus interruption for > 28 days	Discontinue Everolimus

* Should HCV flare be confirmed, the guidelines for flare must take precedence (Table 4-4).

Table 4-2**Dosing guidelines for Everolimus-related hematologic toxicities**

Toxicity	Action
Grade 2 thrombocytopenia (platelets <75, \geq 50x109/L)	Interrupt Everolimus until resolution to grade \leq 1 If resolution occurs \leq 7 days, reintroduce Everolimus at the dose level prior to interruption. If resolution occurs $>$ 7 days, or event occurs within 28 days, reintroduce Everolimus at one dose level lower, if available.

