6.0 MEASUREMENT OF EFFECT

6.1 Response Assessment

6.1.1 Definitions

Evaluable for toxicity. All patients will be evaluable for toxicity from the time of their first treatment with study drug.

Evaluable for objective response. Only those patients who have measurable disease present at baseline, have received at least one cycle of therapy, and have had their disease re-evaluated will be considered evaluable for response. These patients will have their response classified according to the definitions stated below. (Note: Patients who exhibit objective disease progression prior to the end of cycle 1 will also be considered evaluable.)

In this study, response and progression will be evaluated using the International Society of Pediatric Oncology Brain, Tumor Subcommittee for the Reporting of Trials criteria shown below with slight modification.³⁴ Response will be assessed by magnetic resonance imaging (MRI) scan every 8 weeks (every 2 cycles) for 1 year, then every 12 weeks.

6.1.2 Complete Response (CR):

Complete disappearance on MRI of all enhancing tumor and mass effect, on a stable or decreasing dose of corticosteroids (or receiving only adrenal replacement doses), accompanied by a stable or improving neurologic examination and must be sustained for at least 4 weeks. If cerebral spinal fluid (CSF) evaluation was positive, it must become negative. CSF negativity has to be confirmed at least two times at consecutive samplings if the CSF was positive.

6.1.3 Partial Response (PR):

Greater than or equal to 50% reduction in tumor size by bi-dimensional measurement on a stable or decreasing dose of corticosteroids, accompanied by a stable or improving neurologic examination and must be sustained for at least 4 weeks.

6.1.4 Minor Response (MR):

Greater than or equal to 25% to < 50% reduction in tumor size by bi-dimensional measurement on a stable or decreasing dose of corticosteroids, accompanied by a stable or improving neurologic examination and must be sustained for at least 4 weeks.

6.1.5 Stable Disease (SD):

Neurologic examination is at least stable and maintenance corticosteroid dose is not increased, and MRI meets neither the criteria for MR nor the criteria for progressive disease and must be sustained for at least 8 weeks.

6.1.6 Stable Disease (SD):

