APPENDIX II: Time and Events Table

Period/Procedure	Screening	Course 1	Courses 2-24 ¹⁰	End of Treatment Visit ¹³	Long Term Follow Up
Study Day/Visit Day	-14 to 1	Day 14 (+/- 4 days)	Day 1 (+/- 7 days)	Within 30 Days	
Informed Consent	X				
Central Review of Pathology and MRI¹	X				
AE Assessment	X		X	X¹⁴	
Concomitant Medications	X		X	X¹⁴	
Drug Accountability			X	X	
Clinical procedures					
Physical Exam	X		X	X	
Vital Signs	X		X	X	
Medical History	X				
Performance Status	X		X	X	
Neurologic Exam	X		X	X	
Pulse Oximetry²	X		X		
Laboratory procedures					
CBC w/ Diff³	X		X	X	
Blood Chemistry⁴	X		X	X	
Coagulation⁵	X		X	X	
Pregnancy Test (HCG)⁶	X		X	X	
Hepatitis (If Required)^{7,8}	X			X	
Everolimus PK Test⁹		X			
Disease Assessment & Outcomes					
Imaging (MRI)¹¹	X		X*¹¹	X	
Lumbar Puncture (optional)¹²	X		X	X	
Survival Follow Up & Other Treatment					X¹⁵

- 1 Central review of pathology/MRI should be completed concurrently with registration, but is not required before starting therapy.
- 2 If pulse oximetry is less than 93% on room air patient should get a CXR monthly until pulse oximetry is >93%.
- 3 Including CBC with differential
- 4 Including alkaline phosphatase, ALT, AST, total bilirubin, calcium, phosphorus, BUN, creatinine, total protein, albumin, glucose, potassium, sodium, chloride, bicarbonate, uric acid, LDH, and lipid panel (LDL, total cholesterol, triglycerides)
- 5 Including PT/PTT/INR
- 6 For females of child bearing potential, urine or serum pregnancy test as per your institutional guidelines. See Section 3.1.12 for further details.
- 7 Including HBsAg, HBsAb, HBcAb, Hep C RNA. See Protocol Section 3.2.14 for details.
- 8 Patients who test positive for hepatitis B antibodies without receiving prior vaccination will be monitored for HBsAg every 4 weeks.
- 9 PK testing should also be performed 2 weeks post any Everolimus dose adjustment or any CYP3A4 concomitant medication administration/dose adjustment. See Protocol Section 5.2.4 for details.
- 10 Courses are 28 days in length. Each subsequent course following course 1 should begin within 7 days of the end of the prior course.
- 11 MRI of the brain and spine will be performed at the beginning of courses 3, 5, 7, 9, 11, 13, 16, 19, 22, and at the end of treatment visit (after course 24). This assessment should be performed on day 1 of these courses as possible, but may be performed up to 7 days prior to starting these courses if necessary.

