APPENDIX III: Patient Drug Diary

Patient Drug Diary – CRAD001CUS224T

Instructions: Please fill out the diary every day using the format given in the example below.

DAY	DATE	TIME	DOSE	NUMBER OF CAPSULES?			COMMENTS
				2 mg	3 mg	5 mg	
1	9/12/09	7:10 AM PM	8 mg	-	1	1	He felt nauseated after taking pills.

DAY	DATE	TIME	DOSE	NUMBER OF CAPSULES?			COMMENTS
				2 mg	3 mg	5 mg	
1		: AM PM					
2		: AM PM					
3		: AM PM					
4		: AM PM					
5		: AM PM					
6		: AM PM					
7		: AM PM					
8		: AM PM					
9		: AM PM					
10		: AM PM					
11		: AM PM					
12		: AM PM					
13		: AM PM					
14		: AM PM					
15		: AM PM					
16		: AM PM					
17		: AM PM					
18		: AM PM					
19		: AM PM					
20		: AM PM					
21		: AM PM					
22		: AM PM					
23		: AM PM					
24		: AM PM					
25		: AM PM					
26		: AM PM					
27		: AM PM					
28		: AM PM					

This patient diary is complete and accurate to the best of my knowledge.

Signature of parent/guardian: _____ Date: _____

This section for Local Study Site Use Only (not to be completed by parent/guardian):

Patient ID: _____ Institution Name: _____

Course #: _____ Dosing Height: _____ Dosing Weight: _____ BSA: _____

This patient diary has been verified for accuracy by (physician) _____ on _____ / _____ / _____

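### MRI dates follow course numbers that may slip by up to 7 days per course, so the stated 8-week interval can reach 10 weeks and scan timing depends on treatment delays

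*Combined protocol and SAP*

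**What the plan says.** **Scan timing.** Section 6.1.1 has response assessed by MRI "scan every 8 weeks (every 2 cycles) for 1 year, then every 12 weeks". Section 5.2.2 opens in calendar months but then fixes the scans by course: before courses 3, 5, 7, 9, 11, 13, 16, 19 and 22, and at the end of treatment after course 24. Footnote 11 of Appendix II repeats that list and allows the scan up to 7 days before the course starts.

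**Course timing.** Section 4.1: "Each course of therapy will last for 28 days for up to 24 courses". Appendix II footnote 10: "Each subsequent course following course 1 should begin within 7 days of the end of the prior course". This allowance is not limited to toxicity.

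**Dosing and holds.** Section 4.3.1 has everolimus "administered orally, once daily at the same time every day". Section 4.5: "Continue treatment for up to 2 years, until disease progression or unacceptable toxicity occurs"; Section 4.8 also gives 2 years. Tables 4-1 and 4-2 require discontinuation only once an interruption exceeds 28 days; the non-hematologic row reads "Any non-hematologic toxicity requiring Everolimus interruption for > 28 days". The Appendix III diary has 28 rows.

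**Analysis.** Section 9.3 estimates duration of response, PFS and EFS by Kaplan-Meier.

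**The concern.** Two cycles equal 8 weeks only if each course starts the day after the previous one ends. Footnote 10 measures each start from the end of the prior course rather than from Course 1 Day 1, so successive slips add up. The scans, tied to course number, slip with them.

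Two children whose tumors progress on the same day can then have different recorded progression dates because one had course delays. PFS, EFS and duration of response would partly reflect delays. Because the trial has no comparator arm, no internal contrast would reveal this.

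The protocol also does not say whether the course clock runs during a dose hold. A hold of 8 to 28 days across a course boundary is allowed by Tables 4-1 and 4-2, but it can meet footnote 10 only if the clock keeps running.

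**Working it through.** **1. Reproduce the stated intervals.** Inputs: 28-day courses (4.1), gap g of 0 to 7 days (footnote 10), scan list (5.2.2). Start of course c, in days after Course 1 Day 1, is (c − 1) × (28 + g).

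With g = 0, two courses are 56 days (8 weeks) and three are 84 days (12 weeks). Both figures in 6.1.1 reproduce.

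**2. Apply the permitted gap.**

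| Scan before course | g = 0 | g = 7 |
|---|---|---|
| 3 | day 56 | 2 × 35 = day 70 |
| 5 | day 112 | 4 × 35 = day 140 |
| 7 | day 168 | 6 × 35 = day 210 |
| 13 | day 336 | 12 × 35 = day 420 |

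The year-1 interval becomes 70 days (10 weeks) and the three-course interval 3 × 35 = 105 days (15 weeks). Adding the 7-day MRI window, two successive year-1 scans can be 70 + 7 = 77 days apart.

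**3. Check against the 2-year limit.** 24 courses with full gaps last 24 × 28 + 23 × 7 = 672 + 161 = 833 days, which exceeds 730. Completing 24 courses within 730 days leaves 730 − 672 = 58 gap days, about 2.5 per gap. Day 420 for the pre-course-13 scan is still reachable, because it uses 12 × 7 = 84 gap days and falls well inside 2 years. Such a child would reach the limit before finishing course 24 (672 + 84 = 756 days).

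**4. Holds.** If a 28-day hold in course 1 or 2 stops the course clock, the first scan moves from day 56 to 56 + 28 = day 84. If the clock runs, it stays at day 56.

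**5. Effect on reported PFS.** Assumptions, not in the documents: exponential progression times, detection at scheduled scans only, and progression dated at the first scan after it occurs. Reported PFS at day t is then the true survival at the last scan on or before t, with S(d) = 0.5^(d/m). For a true median of 4 months, m = 4 × 30.4375 = 121.75 days.

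- Day 183, zero gaps: last scan day 168, S = 0.5^(168/121.75) = 38%. Seven-day gaps: last scan day 140, S = 45%. The true value is 35%.
- Day 215, zero gaps: last scan still day 168, 38%. Seven-day gaps: last scan day 210, S = 30%. The true value is 0.5^(215/121.75) = 29%.
- Reported median is the first scan after day 121.75: day 168 with zero gaps, day 140 with 7-day gaps.

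With gaps drawn uniformly from 0 to 7 days, simulation (300,000 draws) gives:

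| True median 4 months | Zero gaps | Random 0–7 | All 7 days |
|---|---|---|---|
| PFS at day 183 | 38% | 47% | 45% |
| PFS at day 215 | 38% | 34% | 30% |
| Reported median (days) | 168 | 133 | 140 |
| Mean detection lag (days) | 31 | 35 | 39 |

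For true medians of 3 to 8 months, 6-month PFS is 5 to 9 points above the zero-gap schedule, and 12-month PFS is between 2 points below and 2 above. The reported median can also lengthen. With a true median of 3 months (91.3 days), the first later scan is day 112 with zero gaps and day 140 with 7-day gaps.

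**The case against.** **What stands.** Ten weeks is a permitted maximum, and 6.1.1 already shows that 8 weeks is intended. The model leaves out detection routes the protocol provides: neurologic examination is monthly (5.2.1), MRI is also done on clinical indication (5.2.2), and progression can be declared on neurologic worsening, new CSF positivity or a rising corticosteroid requirement (6.1.7). These would shrink the shifts by an amount the documents do not let us calculate. PFS, EFS and duration of response are secondary and descriptive in 18 children, with no PFS threshold. The two-stage calculation in 9.2 is unaffected.

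**Stronger readings the documents do not support.**

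- A reader might infer that gaps lengthen every time-to-event estimate. Step 5 shows otherwise: the rise at 6 months occurs because the pre-course-7 scan crosses day 183, while the day-215 figure and, with a true 4-month median, the reported median both fall. For duration of response, 6.1.11 makes both start and end assessment dates, so lengthening cannot be presumed.
- A reader might infer that footnote 10 contradicts daily dosing and leaves children off drug for 7 of every 35 days. The footnote never says drug is withheld. It can be read as a scheduling tolerance like the ±7-day visit window in the same table. Handling of those days is undefined rather than contradictory.
- A total of 161 gap days over 24 courses is not available within the 2-year limit.
- The 28-row diary ("Please fill out the diary every day using the format given in the example below") is weak evidence of a planned break, since 4.4.3 calls it an example and also requires tablet reconciliation at each visit.

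**Conclusion.** The inconsistency is real. MRI timing is stated in calendar weeks in one place and tied to a course count that may drift in another, and the two agree only with zero gaps. The permitted year-1 interval reaches 10 weeks and the pre-course-13 scan can be 84 days late, whichever way dosing between courses is read.

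The statistical consequence is modest: about 4 to 8 more days of mean detection lag, and shifts of several points in landmark PFS or of weeks in the median, in either direction. These sizes rest on exponential progression, scheduled-scan detection and assumed gap patterns. Actual gaps, and their causes, are unknown.

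A calendar schedule would not remove the error from periodic scanning; at day 215 the zero-gap schedule itself reports 38% against a true 29%. It would make the scan pattern the same for all children and independent of delays. The change is worth making because it is nearly free, not because the trial's conclusion is threatened.

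**What to change.** In 5.2.2, 6.1.1 and footnote 11, set on-treatment MRI due dates from Course 1 Day 1 at weeks 8, 16, 24, 32, 40, 48, 60, 72 and 84, independent of course number, gaps and holds, with the existing 7-day window. Keep the end-of-treatment MRI as now stated. Say whether a child still on treatment at week 96 also has a scan then, as the 12-week interval in 6.1.1 would imply.

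Separately, reconcile footnote 10 with 4.1, 4.3.1, the 2-year limit in 4.5 and 4.8, and the hold rules in Tables 4-1 and 4-2. The text should state how days between courses are handled and recorded, and whether the course clock runs during a hold. No dosing rule is proposed here.

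The cost is wording. The nine on-treatment scans are the same number as now, and with zero gaps they fall on the same dates. After a delay an MRI may not coincide with a course visit.

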APPENDIX III: Patient Drug Diary

Patient Drug Diary – CRAD001CUS224T

Instructions: Please fill out the diary every day using the format given in the example below.

DAY	DATE	TIME	DOSE	NUMBER OF CAPSULES?			COMMENTS
				2 mg	3 mg	5 mg	
1	9/12/09	7:10 AM PM	8 mg	-	1	1	He felt nauseated after taking pills.

DAY	DATE	TIME	DOSE	NUMBER OF CAPSULES?			COMMENTS
				2 mg	3 mg	5 mg	
1		: AM PM					
2		: AM PM					
3		: AM PM					
4		: AM PM					
5		: AM PM					
6		: AM PM					
7		: AM PM					
8		: AM PM					
9		: AM PM					
10		: AM PM					
11		: AM PM					
12		: AM PM					
13		: AM PM					
14		: AM PM					
15		: AM PM					
16		: AM PM					
17		: AM PM					
18		: AM PM					
19		: AM PM					
20		: AM PM					
21		: AM PM					
22		: AM PM					
23		: AM PM					
24		: AM PM					
25		: AM PM					
26		: AM PM					
27		: AM PM					
28		: AM PM					

This patient diary is complete and accurate to the best of my knowledge.

Signature of parent/guardian: _____ Date: _____

This section for Local Study Site Use Only (not to be completed by parent/guardian):

Patient ID: _____ Institution Name: _____

Course #: _____ Dosing Height: _____ Dosing Weight: _____ BSA: _____

This patient diary has been verified for accuracy by (physician) _____ on _____ / _____ / _____
